### 5.1.9 Methods for Handling and imputation of Missing Data

For medications and procedures, imputation of missing or partial dates will be done to identify concomitant medications and procedures as follows:

 If the start date of the medication/procedure is unknown (i.e. complete missing date), the worstcase scenario will be assumed. The medication/procedure will be considered as both a prior medication/procedure and a concomitant medication/procedure.

- If the month and the day of the start date of the medication/procedure are missing, the month and the day will be imputed to January, 1st of the year specified.
- If the day of the start date of the medication/procedure is missing, the day will be imputed to the first day of the month specified.
- If the end date is unknown (i.e. missing), the date will be kept as missing however the medication/procedure will be considered concomitant.
- If the month and the day of the end date of the medication/procedure are missing, the month and the day will be imputed to December, 31st of the year specified.
- If the day of the end date of the medication/procedure is missing, the day will be imputed to the last day of the month specified.

The original incomplete, missing or partial dates and corresponding imputed dates will be presented in the listings.

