### 4.5 Protocol Deviations

The protocol deviations, classified as major by Vifor in the Project Specific Protocol Deviation List version 7.0 dated 26 November 2021 will be identified for all subjects by either site monitoring, medical review processes or programming and confirmed prior to or at the Data Review Meeting at the latest.

Population	Category	Sub category	Description	Vifor's	l
------------	----------	--------------	-------------	---------	---

				classification
PPS	2. Study Conduct/ Procedures	A. Inclusion/ Exclusion Criteria	Failure to complete inclusion criteria #1	Major
PPS	2. Study Conduct/ Procedures	B. Screening	Safety and Haematology     Laboratory samples not taken     at screening and baseline visit     prior to first dosing	Major
PPS	2. Study Conduct/ Procedures	B. Screening	9. Safety and Haematology Laboratory samples: results needed for eligibilty confirmation missing at screening and baseline visit prior to first dosing.	Major
PPS	2. Study Conduct/ Procedures	B. Screening	21. Randomization errors (e.g. incorrect randomization process interaction with IVRS system) resulting in incorrect allocation of the study therapy	Major
PPS	2. Study Conduct/ Procedures	D. Study Restrictions/ Withdrawal Criteria	Non-compliance with protocol restrictions (e.g. use of prohibited medication or prohibited treatment therapy)	Major
PPS	2. Study Conduct/ Procedures	D. Study Restrictions/ Withdrawal Criteria	2. Non-compliance with subject withdrawal criteria defined in the protocol (i.e. subject continued in study but should have been withdrawn).	Major
PPS	2. Study Conduct/ Procedures	E. Dose Formulation/ Dose Administration	2. Incorrect IMP dose intake: Patient took less than 80% of prescribed doses or took more than 105% of prescribed doses. To be assessed during the course of the study (V3 to V8)	Major
PPS	2. Study Conduct/ Procedures	E. Dose Formulation/ Dose Administration	3. Incorrect subject IMP kit given OR wrong dose regimen (total daily dose) assigned based on screening body weigth	Major

All protocol deviations will be presented in the data listings, including the nature of the protocol deviation, non-important or important.

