### 5.4 Prior and Concomitant Medications and Procedures

All medications will be coded using the current version of the World Health Organization Drug (WHO Drug) dictionary [Mar2020 B3G].

Prior medications will be defined as all medications taken before the first dose of study drug with a stop date prior to the first dose of study drug.

Concomitant medications will be defined as all medications with a start date before, on or after the first dose of study drug and with a stop date on or after the first dose of study drug or with a missing stop date.

Prior and concomitant medication will be summarized by number and percentage of subjects. If any prior or concomitant medication is classified into multiple ATC classes, the medication will be summarized separately under each of these ATC classes. The summary tables will be sorted by decreasing frequency of treatment group and decreasing frequency of drug in a given drug class (therapeutic subgroup [2nd level of the ATC classification], chemical subgroup [4th level of the ATC classification] and Preferred Name). In case of equal frequency regarding drug, alphabetical order will be used. A same medication or procedure during the study for one subject will be counted once.

Prior procedures will be defined as all procedures performed before the first dose of study drug with a stop date prior to the first dose of study drug.

Concomitant procedures will be defined as all procedures with a start date before, on or after the first dose of study drug and with a stop date on or after the first dose of study drug or with a missing stop date.

Prior and concomitant procedures will be summarized by displaying the counts and percentages of subjects with at least 1 prior procedures, 1 concomitant procedures and the number of prior and concomitant procedures.

Listings with all prior and concomitant medications and procedures will be provided including the flag for prior, concomitant. Study days will be displayed with start and stop dates.

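### SAP 5.1.9 labels any medication or procedure with a completely missing start date as concomitant even when its stop date is known to precede the first dose, which contradicts SAP 5.4

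*SAP*

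**What the plan says.** SAP 5.1.9 gives the date rules used to identify concomitant medications and procedures. For a completely missing start date: "If the start date of the medication/procedure is unknown (i.e. complete missing date), the worstcase scenario will be assumed". The result is then stated: "The medication/procedure will be considered as both a prior medication/procedure and a concomitant medication/procedure". The stop date is not mentioned.

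Partial start dates are handled differently: "If the day of the start date of the medication/procedure is missing, the day will be imputed to the first day of the month specified". When month and day are both missing, 1 January of the stated year is used. Partial stop dates go to the last day of the month or to 31 December.

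SAP 5.4 defines the two classes. Prior medications are those "taken before the first dose of study drug with a stop date prior to the first dose of study drug". Concomitant medications may start at any time and are those "with a stop date on or after the first dose of study drug or with a missing stop date". The definitions for procedures have the same form.

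Protocol 8.1.6 requires treatments prescribed up to at least 3 months before consent to be entered in the eCRF, whether or not they are still ongoing. Protocol 5.3 (exclusion 2) and 6.8 allow a subject who stopped iron chelation early enough before randomisation (a 4-week limit) to enter the trial.

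**The concern.** SAP 5.4 makes prior and concomitant mutually exclusive and lets the stop date decide. SAP 5.1.9 assigns both labels whenever the start date is completely missing. SAP section 1 ranks the SAP above the protocol, but nothing ranks 5.1.9 against 5.4, so the programmer has to choose.

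Following 5.1.9 as written reports as on-study a treatment that the data show had ended. The case is plausible here. A chelator stopped before the trial has to be recorded, and eligibility turns on when it was stopped. No eligibility rule turns on when chelation began. Chelation bears directly on the iron parameters, so a false on-study entry could mislead someone reading the iron results beside the concomitant-medication table.

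**Working it through.** The plan states no figure on this point. The check sets the two rules side by side.

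**Inputs.** SAP 5.4: class determined by stop date. SAP 5.1.9: dual label if the start date is completely missing. SAP 2.4 and protocol 12.3: at least 20 subjects in Cohort I, randomised 8:8:4, and up to 10 in Cohort II, randomised 4:4:2. Protocol 5.1: approximately 36 randomised in total.

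**Step 1: classify every case with a completely missing start date.** An item that stopped before the first dose must have been taken before it, so the 5.4 definition of prior is met without a start date. The 5.4 definition of concomitant accepts any start date. SAP 5.4 therefore gives one answer in each row.

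| Stop date | SAP 5.4 | SAP 5.1.9 | Disagreement |
|---|---|---|---|
| Before first dose | Prior only | Prior and concomitant | Concomitant label is wrong |
| On or after first dose | Concomitant only | Prior and concomitant | Prior label conflicts with 5.4 |
| Missing | Concomitant only | Prior and concomitant | Prior label conflicts with 5.4 |

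The false on-study label arises in one of the three rows, where the stop date already settles the question.

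**Step 2: check the limits of the rule.** If the site knows only the year or the month of starting, the start date is imputed and 5.4 then classifies by stop date. A chelator with a partial start and a pre-dose stop comes out as prior only, which is correct.

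**Step 3: compare with the adverse-event rule in the same section.** For a missing adverse-event start, the imputed date is the minimum of several candidates, one of which is the latest possible stop date. A known stop therefore caps the imputed start. The medication and procedure rule has no such cap.

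**Step 4: illustrate the size of one affected record.** The number of such records cannot be derived from the documents, so this takes one record in one arm.

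- Cohort I at its minimum of 20: placebo 1/4 = 25%; each active arm 1/8 = 12.5%.
- Upper end, Cohort II analysed separately at its full 10: placebo 1/2 = 50%; each active arm 1/4 = 25%.
- Lower end, all 36 in one analysis at the same ratio: placebo 36 × 4/20 = 7.2, so 1/7.2 ≈ 14%; each active arm 36 × 8/20 = 14.4, so 1/14.4 ≈ 7%.

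These are percentages of subjects in a descriptive table. They are not effects on an endpoint.

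**The case against.** The best defence is that 5.1.9 announces a worst case, that over-counting concomitant therapy is the cautious direction, and that little depends on it. Much of this stands. All analyses are descriptive with no tests (SAP 3.2 and 5.1.5). Original and imputed dates both appear in the listings, so an error can be seen. The baseline chelation item in SAP 5.2 combines prior and ongoing use, so it would not change. Censoring of efficacy and PK data runs from the first transfusion date (SAP 4.2 and 4.3), not from this flag.

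The worst-case argument fails for the row at issue. A worst case resolves uncertainty, and a stop date before the first dose leaves none about on-study use.

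Four stronger readings are tempting but not supported:

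- **That chelators stopped before the trial are affected in general.** Only a completely missing start date triggers the rule, and the documents do not say how often that occurs.
- **That affected subjects are reported as taking prohibited therapy and lose their place in the per-protocol set.** SAP 4.5 does list "Non-compliance with protocol restrictions (e.g. use of prohibited medication or prohibited treatment therapy" as a major deviation, and programming is one way of finding deviations. But nothing links that check to the 5.1.9 label, and deviations are confirmed at the latest at the Data Review Meeting. Chelation stopped less than 4 weeks before randomisation is restricted in its own right, so flagging that case would not be an error of the date rule.
- **That the missing-end-date rule is also contradictory.** It reads "If the end date is unknown (i.e. missing), the date will be kept as missing however the medication/procedure will be considered concomitant", and 5.4 says the same. Whether an old splenectomy or transfusion would be caught depends on how the CRF records procedure end dates, which the documents do not show.
- **That hydroxyurea raises the same problem.** Stable use for 6 months or more is allowed (protocol 6.8), so an ongoing course is correctly concomitant and is not a deviation.

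**Conclusion.** The contradiction is real and the rule is wrong as written. For an unknown start and a known pre-dose stop, SAP 5.1.9 produces a concomitant label that SAP 5.4 and the recorded date both rule out. The documented result is an extra count in the concomitant summary and a wrong flag in the listings.

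Severity is minor. At the minimum Cohort I size one affected record moves a table entry by 25 percentage points in placebo or 12.5 in an active arm. Those figures assume exactly one record in the arm and no enrolment beyond 20, and they shrink as the cohort grows. The dual label also conflicts with 5.4 in the other two rows, but there it adds only a superfluous prior entry.

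**What to change.** Amend SAP 5.1.9 so that, when the start date is completely missing, the item is classified by its known or imputed stop date. A stop before the first dose means prior only. The worst case applies only when the stop date is on or after the first dose, ongoing or missing.

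In the same edit, bring the dual label into line with 5.4. Either call those remaining items concomitant only, as 5.4 already implies, or state in 5.4 that they are a deliberate exception counted in both tables.

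The existing imputation of partial stop dates to the end of the month or year can stay. It already leans towards concomitant when the stop date is vague, so no genuine on-study use is lost.

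The cost is a sentence or two in the SAP and a small change to the derivation program, with no real downside.

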### **Subject Disposition**

Subject disposition data will be collected on the CRF when a subject completed or discontinued from the study. The patient disposition data will be summarized. The following data will also be presented in the listings:

- · Date of informed consent or assent.
- Date of randomisation.
- Date of completion/or withdrawal

For diagnosis, imputation of partial dates will be done as follows:

- If the date of the diagnosis is unknown (i.e. complete missing date), the date will not be imputed.
- If the month and the day of the date of the diagnosis are missing, the month and the day will be imputed to January, 1st of the year specified.
- If the day of the date of the diagnosis is missing, the day will be imputed to the first day of the month specified.

### Adverse events

Missing and/or incomplete dates/times for AEs are imputed in a manner resulting in the earliest onset or the longest duration during the treatment period, taking additionally into account that the start

date/time should not be after the stop date/time. Stop dates/times will not be imputed if the AE is ongoing. This will be done as follows:

For a missing/incomplete start date/time the minimum of the following will be imputed:

- The maximum of the earliest possible start date/time and the date/time of first study medication administration.
- The latest possible start date/time.
- The latest possible stop date/time.

For a missing/incomplete stop date/time the maximum of the following will be imputed:

- The minimum of the latest possible stop date/time and the date/time of last study medication administration.
- The earliest possible stop date/time.
- The earliest possible start date/time.

The earliest/latest possible date is defined as:

- The date itself if it is complete.
- The date of the first/last day of the month, if month and year are available but day is missing.
- The date of the first/last day of the year, if year is available but day and month are missing.
- A very early/late date, e.g., 01JAN2000 (01JAN2100), if the date is completely missing.

The imputation method will only be used to determine treatment emergence and to determine the time of the event relative to the first administration of study medication. A worst-case approach will be followed in the event of missing severity or causality data. If the severity is missing, 'Severe' will be imputed. If causality data is missing, 'Related to study medication' will be imputed. In the event that no coding information is available for a specific AE, the AE will be presented as an 'Uncodable Event' in summary tables.

### **Clinical Laboratory Evaluations**

TSAT should be calculated as Total Iron /Total Iron Binding Capacity (TIBC) X 100 as per current SSW, while TIBC is calculated as sum of Total Iron and Unsaturated Iron Binding Capacity (UIBC).

UIBC values reported below the lower level of quantification (LLOQ) i.e. "< 5.0 µmol/L" should be imputed to zero, to avoid that TSAT values will be reported as "Unable to calculate".

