5. SELECTION AND WITHDRAWAL OF SUBJECTS

5.1 Number of Subjects

In total, approximately 36 subjects are planned to be randomised in order to have up to 30 male and female adult and/or adolescent NTDT subjects completing the trial. For the initial safety review in Cohort I, in order to keep a required 4:4:2 ratio, if 1 adult NTDT subject prematurely discontinues the study for reasons other than safety before completing the study Week 8 visit, he or she will be replaced. Accordingly, for the initial safety review of adolescent NTDT subjects in Cohort II, in order to keep a 2:2:1 ratio, if 1 adolescent NTDT subject prematurely discontinues the study for reasons other than safety before completing the study Week 8 visit, he or she will be replaced. Subjects included to replace subjects in the initial safety reviews of Cohort I and Cohort II will receive the same treatment as the subjects they are replacing.

For the remaining subjects in Cohort I and Cohort II, no additional subject(s) will be enrolled. Based on an anticipated drop-out rate of approximately 20%, it is estimated that approximately 6 subjects will be additionally randomised.

For detailed justification of the sample size please refer to Section 12.2.

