12.3 Randomisation

All subjects enrolled must be identifiable throughout the study. The Investigator will maintain a list of subject numbers and subject names to enable records to be found at a later date.

Randomisation of the subject will be performed before start of treatment with study drug using a validated centralised procedure (IWRS). Randomisation will be performed based on pre-defined randomisation list for each cohort.

Subjects eligible for randomisation will receive a randomisation number. Randomised subjects who terminate their study participation for any reason regardless whether the study drug was taken or not, will retain their randomisation number. The next subject will be given the next randomisation number.

The subjects will be randomised according to the following scheme:

- In Cohort I, at least 20 subjects will be randomised into a 8:8:4 distribution to VIT-2763 QD or VIT-2763 BID, or placebo respectively.
- In Cohort II, up to 10 subjects will be randomised into a 4:4:2 distribution to VIT-2763 QD or VIT-2763 BID or placebo, respectively.

VIT-2763 dose will be adapted to the body weight of the subject:

- Body weight of 40 kg to 59 kg: VIT-2763 dose of 60 mg QD or 60 mg BID, or corresponding placebo.
- Body weight of 60 kg to 100 kg: VIT-2763 dose of 120 mg QD or 120 mg BID, or corresponding placebo.

The randomisation list in each cohort will be generated using an algorithm that will ensure that for Cohort I and Cohort II, the first 10 and 5 subjects will be randomised with a 4:4:2 and 2:2:1 distribution, respectively, for the safety review of each cohort.

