### 2.6.2 Secondary Endpoint(s)

- Assessment of iron parameters (total serum iron, serum ferritin, serum transferrin, unsaturated iron binding capacity, calculated TSAT, from baseline over a 12-week period (absolute and change from baseline)).
- PK parameters: individual estimates of Cmax, clearance, distribution volume, AUC will be
  obtained using a population PK approach in adult and adolescent subjects combined with
  suitable mathematical/statistical analysis, using nonlinear mixed-effects modelling. Sparse
  sampling for determination of VIT-2763 plasma concentration following multiple dosing will be
  obtained from pre-dose trough to 3 or 4 hours post-dose at selected study visits.

\*\* For ECG, baseline value will be defined during Screening visit and assessment recorded at the Visit 3 (Day 1) will be presented as "Baseline 2h post-dose".

 Only in subjects who consent in writing to provide blood samples for biomarkers and genotyping, whole blood samples will be taken and stored for later determination of biomarkers and genotyping. The biomarker and pharmacogenetic endpoints will be defined at a later time point, taking into account further scientific and clinical data.

•

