### 5.1.1 Standard Descriptive Statistics

### Continuous Variables

Unless specified otherwise, the following standard descriptive statistics by treatment group will be obtained for continuous variables: number, mean, standard deviation, median, inter-quartile range and range. The minimum and maximum will be reported to the same number of decimal places as the raw data recorded in the database. Mean, median, inter-quartile range will be displayed to one more decimal place than collected value and standard deviation will be displayed to two more decimal place than collected value.

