### 5.1.2 Definition of Baseline, Visits and Visit Windows

The baseline will be defined as the last available (non-missing) value before the first administration of study drug except for parameters listed below:

- PD measurements (serum iron, serum ferritin, unsaturated iron binding capacity, calculated transferrin saturation). Baseline will be collected during screening period within the biochemistry sample.
- For following parameters, the baseline will be defined as the value at Visit 3 2h post-dose:

PD measurements (serum transferrin).

Study day 1 is defined as the day of the first study drug administration. For analysis relative day, if considered date less than first study drug administration date, then analysis relative day will be considered date minus first study drug administration date, otherwise, it will be considered date minus first study drug administration date + 1.

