### 5.7.2 Clinical Laboratory Evaluations

A list of all protocol specified clinical laboratory tests are given in Appendix A and will be performed at screening, baseline, week 1, week 2, week 4, week 8 and week 12 for haematology, biochemistry and urinalysis and at screening, baseline, week 4 and week 12 for coagulation in accordance with the Schedule of Events in section 2.3. For analyses, Planned Assessment Windows (see Section 2.2.3) are defined for each visit.

Descriptive statistics will be performed for laboratory parameters on a continuous scale for the scores and change from baseline for each visit split by treatment group.

If multiple tests were performed at baseline, the latest non-missing measurement prior to the first administration of study treatment will be used for the baseline value. For multiple tests at post-baseline visits occurring during the same visit window, the closest measurement will be used for the analyses and summary tables. When two measurements are exactly equidistant to the exact visit date, the later will be used for the analyses and summary tables. Laboratory values expressed as 'less than" or "greater than" will be imputed using the next numerical value (i.e. '<2.00' imputed as 1.99, ">0.3" imputed as 0.4).

Shift tables for the haematology and biochemistry laboratory parameters comparing values low, normal and high using the standard reference ranges will be presented for the baseline laboratory measurement versus the endpoint measurement for each subject. The number and percentage of subjects with abnormal values for each analyte will be summarized at each analysis visit. Abnormal values for each analyte will be determined using normal ranges provided by the central laboratory. The descriptive analysis by visit will also include an overall summary. If any of the subject's post-baseline measurements are abnormal (low or high), then the subject is classified as abnormal in the overall summary.

All laboratory results (local and central values) will be listed, including all unscheduled visits.

Only central laboratory parameters will be analysed.

eGFR formula: 186 x (Creatinine/88.4)-1.154 x (Age)-0.203 x (0.742 if female) x (1.210 if black)

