## 5.9 Other Analyses

#### 5.9.1 Iron Pharmacodynamics Analyses

The values and change from baseline results of iron pharmadynamic parameters (serum iron, serum ferritin, serum transferrin, unsaturated iron binding capacity, calculated transferrin saturation) will be summarized and listed by treatment group and timepoints. No formal statistical tests are planned.

For each iron pharmadynamic parameters, the Baseline value is defined as the last non-missing measurement collected/during screening period.

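### Setting UIBC below the LLOQ to zero fixes TSAT at exactly 100%, and the planned TSAT summaries do not show how much of a change comes from that rule

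*SAP*

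**What the plan says.** - **TSAT formula and rule.** SAP 5.1.9, in its part on clinical laboratory evaluations, defines TSAT as total iron over total iron binding capacity (TIBC), times 100, with TIBC the sum of iron and UIBC. A UIBC result below 5.0 µmol/L "should be imputed to zero, to avoid that TSAT values will be reported as" not calculable.
- **Role.** SAP 2.6.2 includes "unsaturated iron binding capacity, calculated TSAT, from baseline over a 12-week period" among the secondary endpoint parameters, both as absolute values and as changes. SAP 5.9.1 adds that "The values and change from baseline results of iron pharmadynamic parameters" are to be summarised and listed by treatment group and time point.
- **Baseline.** For UIBC and calculated TSAT, SAP 5.1.2 states: "Baseline will be collected during screening period within the biochemistry sample".
- **Statistics shown.** SAP 5.1.1 gives "number, mean, standard deviation, median, inter-quartile range and range" for continuous variables.
- **A second rule.** SAP 5.7.2 says that laboratory values carrying a less-than or greater-than sign "will be imputed using the next numerical value"; its example turns <2.00 into 1.99. UIBC is in the Appendix A list of biochemistry parameters.
- **Inference.** SAP 3.2 and 5.1 make every analysis descriptive.

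**The concern.** A UIBC reported as below 5.0 µmol/L can lie anywhere from 0 to 5. The only reason the SAP gives for choosing zero is that TSAT can then be calculated, and any value in that range would achieve this. Zero is the one choice that pushes TSAT to its ceiling and removes its dependence on iron.

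Two distortions follow. A real fall in TSAT disappears when baseline and post-baseline UIBC are both below the LLOQ. A move across the LLOQ is enlarged: a fall when UIBC rises above it, a rise when UIBC drops below it.

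Eligibility sets a floor for TSAT (Protocol 5.3, exclusion of TSAT under 30%) but no ceiling, so highly saturated subjects can enter. The drug is meant to lower iron in plasma, so crossings could be more frequent on active treatment. The same rule in every arm therefore does not guarantee the same effect in every arm.

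Separately, SAP 5.1.9 and 5.7.2 give different numbers for the same UIBC result. Two programmers could follow the SAP and produce different UIBC tables.

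**Working it through.** **Inputs.** From SAP 5.1.9: TSAT(Fe, U) = 100 × Fe/(Fe + U), LLOQ 5.0 µmol/L, imputed value 0. The documents give no serum iron or TIBC levels for this population, so those below are assumptions. There is no TSAT figure in the plan to reproduce.

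**1. Imputed value.** TSAT(Fe, 0) = 100 × Fe/Fe = 100% for any positive Fe.

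**2. Largest artificial part of a step across the LLOQ.** This arises when true UIBC is just under 5: 100 − 100 × Fe/(Fe + 5) = 500/(Fe + 5).

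| Assumed iron (µmol/L) | TSAT at UIBC 5.0 | Largest artificial part (points) |
|---|---|---|
| 20 | 80.0% | 20.0 |
| 30 | 85.7% | 14.3 |
| 40 | 88.9% | 11.1 |
| 50 | 90.9% | 9.1 |

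**3. Crossings with stable TIBC, assumed 45 µmol/L (iron = 45 − UIBC).**

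| True UIBC, baseline then later | True change | Reported change | Artificial share |
|---|---|---|---|
| 4 then 6 | −4.4 | −13.3 | 67% |
| 4 then 10 | −13.3 | −22.2 | 40% |
| 1 then 6 | −11.1 | −13.3 | 17% |
| 0 then 10 | −22.2 | −22.2 | 0% |

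The excess depends only on how far the true sub-LLOQ value lies above zero.

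**4. Both visits below the LLOQ.** The reported change is 100 − 100 = 0. With TIBC stable at 45, if UIBC goes from 0 to 4.9 then iron goes from 45 to 40.1, and the true change is 100 × 40.1/45 − 100 = −10.9 points.

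**5. Effect on a group mean.** In Cohort I "at least 20 subjects will be randomised into a 8:8:4 distribution", so 20 adults give 4 on placebo. Overall "approximately 36 subjects are planned to be randomised", and one fifth of 36 is 7.2, about 7 on placebo if adults and adolescents share one table (SAP 5.1 pools them when fewer than 5 adolescents are randomised). At iron 30, one affected value moves the mean by at most 14.29/4 = 3.6 or 14.29/7 = 2.0 points.

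**6. The two rules.** For a result of <5.0, SAP 5.1.9 gives 0 and SAP 5.7.2 gives about 4.9. At iron 30 the corresponding TSAT is 100% or 100 × 30/34.9 = 86.0%.

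**7. What a repeat at 5.0 µmol/L can show.** It gives the opposite bound for each TSAT value. It does not bound the change for a subject below the LLOQ twice. In the case in step 4 it gives 100 × 40.1/45.1 − 100 × 45/50 = 88.9 − 90.0 = −1.1, against a true −10.9.

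**The case against.** - **Affected values mark themselves.** A quantified UIBC is at least 5, so TSAT can then be no higher than 100 × Fe/(Fe + 5), which is below 100%. An exact 100% can come only from the imputation. Iron parameters and all laboratory results are to be listed (SAP 5.9.1 and 5.7.2). This stands: a reader might infer that imputed values cannot be traced, and that is wrong. What the listings do not supply is the dependence of the group means and changes on the imputation.
- **Extreme ranges are algebra, not realistic uncertainty.** With iron 40 then 30 and both UIBC values free between 0 and 5, the change could be anything from −14.3 to +11.1. The first bound needs TIBC to fall from 40 to 35 µmol/L and the second from 45 to 30. Nothing in the documents supports such falls; Protocol 1.2.3 reports no dose-related effect on serum transferrin over 7 days in healthy subjects. The objection stands against using that range. The stable-TIBC cases above do not need it.
- **Little depends on it.** The rule is pre-specified and common to all arms, and no test or decision uses it. Serum iron, ferritin and transferrin are summarised separately, and medians and quartiles are reported. The TSAT entry limit is practically untouched: with UIBC at 5, TSAT under 30% needs iron below 0.3 × 5/0.7 = 2.1 µmol/L. All of this stands and keeps the point minor.
- **The specific rule prevails over the general one.** That is the natural reading, since SAP 5.1.9 names the analyte, the limit and the reason. But no sentence says so, and Appendix A places UIBC within the scope of SAP 5.7.2.
- **A count or display may exist out of sight.** SAP 5.6.3 is blank in the public copy, and the TSAT formula refers to a source not provided. The statement that none is planned applies only to the visible text.

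**Conclusion.** The concern holds and is minor. It follows from the SAP's own formula that TSAT is 100% whenever UIBC is below the LLOQ, that the reported change is 0 when both visits are below it, and that up to 500/(Fe + 5) points of a crossing can be artificial. That is 9.1 to 20.0 points for one subject if iron is between 50 and 20 µmol/L, an assumed range.

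A reader might go further and conclude that the TSAT results are biased in favour of the drug. The documents do not support that. They give neither iron levels nor the share of UIBC values below the LLOQ, the rule hides some falls and enlarges others, and the excess is nil where true UIBC is near zero. The net effect on group means is unknown and could be nil. What can be said is that the visible plan offers no way to judge it from the summary tables, and that the rule for the UIBC summary is not settled in words.

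**What to change.** 1. Report the number of UIBC values below the LLOQ by arm and visit.
2. Repeat the overall TSAT summary (values and change from baseline) once, with UIBC below the LLOQ set to 5.0 µmol/L. A footnote should say that using the same bound at both visits does not span the full range for subjects below the LLOQ twice. LLOQ/2 is an acceptable alternative, but it does not recover changes that occur wholly below the LLOQ either. Pairing opposite bounds for every subject is not worthwhile: with about 4 to 7 placebo subjects the limits would be too wide to inform.
3. Add one sentence: the SAP 5.1.9 rule for UIBC below the LLOQ applies to both the UIBC and the TSAT summaries and overrides SAP 5.7.2.

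The cost is one sentence, one count row and one extra descriptive table, which need not be repeated by body weight or other subgroup. No test or decision is affected.
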